12.3 Post-ablation Follow-up Visits

The list of assessments is the same for all follow-up visits unless otherwise specified.

At each follow-up visit, the patient will visit the site (or have a tele-visit and/or phone visit when unable to visit the site) and the following assessments will occur:

- Evaluate ECOG performance status (Visit 3 only). After Visit 3, evaluate ECOG, if applicable per site SOC. ECOG may be assessed over the phone.
- Laboratory tests, as follows, if applicable per site SOC:
 - Coagulation tests, including, INR, PT and APTT (or PTT).
 - Liver function tests, including AST, ALT, GGT, albumin, direct and total bilirubin, and total protein.
 - Renal function tests, including BUN, creatinine and electrolytes (sodium, potassium, chloride and bicarbonate).
 - CBC, including differential cell count and platelet count.
 - Genetic markers including: Alpha-fetoprotein (AFP) level, Carbohydrate antigen 19-9 (CA19-9) level, Carcinoembryonic antigen (CEA).
- Record all relevant concomitant medications: Relevant concomitant medications include: chemotherapy, immunotherapy, blood-thinning or coagulation, NSAIDs, those medications used to treat AEs, those used for hepatitis (if concurrently treating), and any others that are relevant in the opinion of the investigator. Relevant concomitant medications may be assessed over the phone.
- QOL questionnaires, using EORTC QLQ-C30 and liver-specific QLQ-HCC18, (Visits 3 through 6). The questionnaires may be administered over the phone, as needed.
- Pain score using the Numeric Pain Rating Scale (Visit 3 only). The questionnaire may be administered over the phone, as needed.
- Technique efficacy evaluation (Visit 3 only).
- Imaging to determine whether there has been a local or regional recurrence of lesion(s). If there is a recurrence, determine soft tissue liver lesion details via CT, MRI, PET, US, and/or X-ray.
 - All SOC scans of the abdomen/liver (CT, MRI, and/or PET) should be submitted to the Sponsor.
- Record relevant concomitant procedures (i.e. liver or lesion-related). Relevant concomitant procedures may be assessed over the phone.

- Record follow-up post-ablation treatment, including the number of successful repeat ablations, if applicable, and if patient has been hospitalized since the procedure. If patient has been re-ablated with NeuWave, record ablation procedure details as outlined in section 19.1, subsection 1.

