1.2 Study Design

This is a multicenter, observational registry that follows patients for a total of up to 5 years from the date of the first liver ablation procedure with either the NEUWAVE Microwave Ablation System or the NEUWAVE Microwave Ablation System with Ablation Confirmation.

This is an “umbrella registry,” which was included as an optional component in other NEUWAVE studies; hence, data from consenting patients who are or will be enrolled in other NEUWAVE soft tissue liver lesion ablation studies will be included in this registry. All other patients will be enrolled and followed prospectively, enrolled retrospectively with prospective, longitudinal follow up, or enrolled retrospectively with all retrospective follow up.

2 Treatment Assignment

This is a single-arm registry where all enrolled patients will be ablated using the NEUWAVE Microwave Ablation System as part of the site’s SOC treatment or per protocol for those patients who are also enrolled in other NEUWAVE studies.

3 Randomization and Blinding Procedures

As this is a single-arm registry, no randomization will occur, and no blinding procedures are required.

4 Interval Windows

Interval windows are provided in the Schedule of Assessments section of the study protocol. No additional windows are planned for analysis purposes.

5 Levels of Significance

No levels of significance are specified as no specific hypotheses about any of the outcomes of interest are being formulated or tested. Two-sided 95% confidence intervals (CI) will be estimated for specific endpoints for descriptive purposes only.

6 Analysis Sets

All Enrolled Set (AES): Consists of subjects who signed informed consent form or retrospectively enrolled with a waiver for signing informed consent form. The AES will be used for disposition of study subjects.

Full Analysis Set (FAS): FAS Consists of subjects who met inclusion/exclusion criteria and to whom the NeuWave Ablation device was utilized during procedure. Primary and secondary endpoints will be analyzed using FAS.

Safety Analysis Set (SAF): SAF Consists of subjects who met inclusion/exclusion criteria and to whom the NeuWave Ablation device was utilized during procedure. Safety endpoints will be analyzed using SAF.

7 Sample Size Justification

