8.4.2 Secondary Endpoints

Secondary endpoints of this registry are:

1. Secondary efficacy rate, defined as the percentage of soft tissue lesions that have undergone successful repeat ablations (target or non-target) following identification of local soft tissue lesion progression. A successful repeat ablation will be defined as ablation of the lesion according to the protocol and covered completely, with an adequate margin, as defined by the performing physician (i.e. the ablation zone completely overlaps or encompasses the lesion plus an ablative margin), as assessed by CT, MRI, PET, US, and/or X-ray, immediately following the procedure.

2. Regional recurrence rate at a separate location in the liver (outside the initial treatment site(s)), evaluated at every visit after ablation of the target lesion(s), and overall evaluation at the 5-year follow-up, as assessed by CT, MRI, PET, US, and/or X-ray.

3. Recurrence-free survival, evaluated at every visit after ablation of the target lesion(s), and overall evaluation at the 5-year follow-up, as assessed by CT, MRI, PET, US, and/or X-ray.

4. Overall survival, evaluated at every visit after ablation of the target lesion(s), and overall evaluation at the 5-year follow-up.
5. Assess economic impact of ablation by capturing procedure-related items such as: complete procedure duration, ablation duration, number of ablations, length of hospital stay, and number and types of probes used.
6. Incidence of adverse events (AEs) (SAEs) that are deemed at least unlikely related to the procedure or device and all serious adverse events (SAEs) from the start of the ablation procedure through the end of the study.
7. Two QOL questionnaires: European Organization for Research and Treatment of Cancer (EORTC) QLQ-C30 and liver-specific QLQ-HCC18.

Note: These two questionnaires were chosen as tools to assess overall health status/quality of life in the patient population with soft-tissue liver lesions.
8. Numeric Pain Rating Score.

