8.5 Analysis of Primary Endpoint

The number and percentage of patients and lesions achieving technical success will be summarized and a two-sided 95% confidence interval will be provided based on Clopper-Pearson's method. Technical success is achieved when the ablation is defined as a complete ablation by the performing physician. Technical success will be summarized at patient level and at lesion level. Technical success is achieved for a patient when all ablated lesions are defined as a complete ablation by the performing physician.

The number and percentage of patients and lesions achieving technique efficacy will be summarized and a two-sided 95% confidence interval will be provided based on Clopper-Pearson's method. Technique efficacy is achieved when the ablation is defined as a complete ablation by the performing physician. Technique efficacy will be summarized at patient level and at lesion level. Technique efficacy is achieved for a patient when all ablated lesions are defined as a complete ablation by the performing physician.

Target lesion recurrence will be summarized at patient level and at lesion level. Time-to-event analysis (survival analysis) using Kaplan-Meier's method will be utilized to estimate the target lesion recurrence rate at 3-month, 6-month, up to 60-month follow up. Cumulative incidence rate will be estimated for target lesion recurrence considering death as a competing risk and estimates will be presented at 3-month, 6-month, up to 60-month follow up. A two-sided 95% CI will be estimated for target lesion recurrence. Subjects who failed technique efficacy will be excluded from the analysis for target lesion recurrence.

First occurrence of a target lesion recurrence at patient level will be considered as the “event” for time-to-event analysis.

First occurrence of a target lesion recurrence at lesion level will be considered as the “event” for time-to-event analysis.

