8.6 Analysis of Secondary Endpoints

The number and percentage of patients and lesions achieving secondary efficacy will be summarized and a two-sided 95% confidence interval will be provided based on Clopper-Pearson’s method. Analysis for secondary efficacy rate includes only repeat ablations for target and non-target lesions.

For patient level analysis – secondary efficacy is achieved for a patient when all re-ablations of target lesions and all re-ablations of non-target lesions are defined as a complete ablation by the performing physician. The denominator for subject level analysis will include subjects who had a re-ablation during visit 3 to visit 14 including unscheduled visits.

For lesion level analysis – secondary efficacy is achieved for a lesion when all repeat ablations of that lesion (target and non-target lesions) are defined as complete ablation by the performing physician. The denominator for lesion level analysis will include lesions that had a repeat ablation during visit 3 to visit 14 including unscheduled visits.

Regional recurrence rates will be estimated at patient level. Time-to-event analysis (survival analysis) using Kaplan-Meier’s method will be utilized to estimate the regional recurrence rate at 3-month, 6-month, up to 60-month follow up. Two-sided 95% CI will be estimated for regional recurrence rate. First occurrence of identification of a new lesion outside the initial treatment site(s) during visit 3 to visit 14 including unscheduled visits at patient level will be considered as the “event” for time-to-event analysis at patient level.

Recurrence-free survival rates will be estimated at patient level. Time-to-event analysis (survival analysis) using Kaplan-Meier’s method will be utilized to estimate the recurrence-free survival rate at 3-month, 6-month, and up to 60-month follow up. Two-sided 95% CI will be estimated for recurrence-free survival rate.

An “event” is defined for recurrence-free survival if any of the following conditions are met:

- a. First occurrence of a target lesion recurrence during visit 4 to visit 14 including unscheduled visits at patient level
- b. Identification of a new non-target lesion during visit 3 to visit 14 including unscheduled visits at patient level

c. Deaths from any cause of a patient during the follow up period

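### Recurrence-free survival counts target-lesion tumour only from Visit 4 without excluding technique-efficacy failures, so tumour seen at Visit 3 is missed in the 3-month estimate and counted late or lost afterwards

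*SAP*

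**What the plan says.** SAP 8.6 gives RFS three kinds of event, and their windows differ:

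- Local, event (a): "First occurrence of a target lesion recurrence during visit 4 to visit 14 including unscheduled visits at patient level".
- New lesion, event (b): "Identification of a new non-target lesion during visit 3 to visit 14 including unscheduled visits at patient level".
- Death, event (c): "Deaths from any cause of a patient during the follow up period".

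Kaplan-Meier is used to "estimate the recurrence-free survival rate at 3-month, 6-month, and up to 60-month follow up".

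The endpoint list in SAP 8.4.2 describes the same outcome as "Recurrence-free survival, evaluated at every visit after ablation of the target lesion(s", and Protocol 6.3 agrees. Visit 3 runs from 7 days to under 3 months and Visit 4 starts at 3 months (Protocol, Schedule of Assessments). The schedule marks recurrence evaluation at Visit 3, and Protocol 12.3 requires, at each follow-up visit, "Imaging to determine whether there has been a local or regional recurrence of lesion(s".

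On the population, SAP section 6 (Analysis Sets) states: "Primary and secondary endpoints will be analyzed using FAS". That set requires eligibility and use of the device, and sets no condition on technique efficacy. SAP 8.5 adds one exclusion: "Subjects who failed technique efficacy will be excluded from the analysis for target lesion recurrence". SAP 8.6 has no counterpart for RFS. SAP 8.7 plans no sensitivity analysis.

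**The concern.** The Visit 3 scan is read for both local and regional disease, but RFS uses only the regional half. A new lesion on that scan is an event; tumour in the ablated lesion on the same scan is not.

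For target lesion recurrence, SAP 8.4.1 also starts at Visit 4, and that works. Tumour at Visit 3 is treated as failure of the ablation, the patient leaves that analysis, and recurrence is counted among the rest. RFS takes over the Visit 4 start without the exclusion that makes it coherent. A patient with target tumour at Visit 3 is then neither removed nor given an event, and stays in the risk set as recurrence-free.

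The registry tests no hypotheses, so its estimates and intervals are its results. Protocol 17.5 names RFS among the outcomes of interest. The error makes RFS look better, most clearly at 3 months.

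**Working it through.** The documents state no expected RFS, technique-efficacy failure rate or power calculation, so there is no planned figure to reproduce. The check has two parts.

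**1. Following one patient through the rules.** Take a patient in the full analysis set with target-lesion tumour on the Visit 3 scan, no new lesion, and alive.

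- Event (a): cannot occur, because the window opens at Visit 4.
- Events (b) and (c): not met.
- Exclusion: none stated for RFS.
- Result at 3 months: at risk and event-free.
- Afterwards, if tumour persists and is recorded as recurrence at Visit 4 or later, the event is counted late. If the lesion is re-ablated and cleared first, no event is counted for that tumour.

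The SAP itself foresees re-ablation in this window: the secondary-efficacy denominator in SAP 8.6 takes re-ablations from Visit 3 onward. The mention of unscheduled visits in event (a) is attached to the Visit 4 to Visit 14 span, so it does not clearly bring in earlier scans.

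**2. Size, on stated assumptions.** Let

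- f = share of patients with residual or regrown target tumour at Visit 3 (assumed 2–10%);
- S = share free of new lesion and death (assumed 95% at 3 months and 70% at 12 months);
- q = share of the affected patients whose target-lesion event is counted from Visit 4 (0 to 1).

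f is taken as independent of S.

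*3 months.* RFS as written = S. RFS with Visit 3 tumour counted = S × (1 − f). Overstatement = f × S.

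| f | As written | Tumour counted | Overstatement | Patients per 1,500 |
|---|---|---|---|---|
| 2% | 95.0% | 0.95 × 0.98 = 93.1% | 1.9 points | 30 |
| 5% | 95.0% | 0.95 × 0.95 = 90.25% | 4.75 points | 75 |
| 10% | 95.0% | 0.95 × 0.90 = 85.5% | 9.5 points | 150 |

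With S = 90% instead, the overstatement is 1.8, 4.5 and 9.0 points.

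*12 months.* Overstatement = f × (1 − q) × S. With f = 10% and S = 70%:

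- q = 1 (all recorded from Visit 4): 0 points.
- q = 0.5: 0.10 × 0.5 × 0.70 = 3.5 points.
- q = 0 (none recorded): 0.10 × 0.70 = 7.0 points. If 10% of these patients had a later local recurrence anyway, this becomes 7.0 × 0.90 = 6.3 points.

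*Scale.* With 1,500 patients and no censoring, the 95% half-width is 1.96 × √(0.95 × 0.05 / 1500) = 1.1 points at RFS 95%, and 1.96 × √(0.70 × 0.30 / 1500) = 2.3 points at RFS 70%. The 1,500 is the enrolment figure in the Protocol Summary and is used only for scale. Censoring would widen both intervals.

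**The case against.** The strongest reply is that the Visit 4 start is deliberate. SAP 8.4.1 defines target lesion recurrence from Visit 4, and RFS reuses that term. A lesion that was never cleared has not recurred; it is a technique failure, and technique efficacy is a primary endpoint reported by patient and by lesion. This explains the window for target lesion recurrence, but not for RFS, where the failures are not removed. Reporting the failure rate in another table does not correct the RFS curve.

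A second reply is that keeping failures in RFS is an inference. No sentence says it, and the full analysis set is also assigned to the primary endpoints, one of which still drops failures. That is fair, but the drop is written for that endpoint alone. If the exclusion were instead read into event (a) only, these patients could never have a target-lesion event, which makes matters worse.

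Three further points stand and limit the claim:

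- Technique efficacy also requires an adequate margin, so a failure need not show tumour. A reader might infer that every technique-efficacy failure is a missed RFS event; the definition does not support that.
- A reader might infer that these patients are counted as recurrence-free throughout follow-up. The documents support this only up to Visit 4. After that the event may simply be late, and the overstatement may be zero.
- RFS is one of eight secondary endpoints, its intervals are descriptive, and the exploratory models in SAP 8.10 do not use it.

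**Conclusion.** The RFS rule is wrong as written. It contradicts the SAP's own endpoint description and Protocol 6.3, and it borrows a window from target lesion recurrence without the exclusion that supports it. The effect is certain for the 3-month estimate, because no target-lesion finding in the Visit 3 window can lower it. Under the assumed 2–10% with target tumour at Visit 3 and 95% free of other events, the overstatement is about 1.9–9.5 points.

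At 12 months it lies between 0 and about 7 points. The upper end needs 10% affected, none recorded from Visit 4, and 70% free of other events. All these rates are assumptions, so the direction is firmer than the size. For a descriptive secondary endpoint this should be fixed, but it does not undermine the registry as a whole.

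**What to change.** Adopt one of two rules in SAP 8.6 before database lock.

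1. **Count it.** Start event (a) at Visit 3, and count residual or recurrent target-lesion tumour on the Visit 3 scan as an RFS event dated to that scan. State that a margin-only technique-efficacy failure showing no tumour is not an event. Add a note that this window differs on purpose from that of target lesion recurrence in SAP 8.4.1. This option agrees with SAP 8.4.2 and Protocol 6.3.
2. **Restrict it.** Limit RFS to patients who achieved technique efficacy, in line with target lesion recurrence. Label the estimate accordingly, report how many patients were excluded, and say how patients without a Visit 3 assessment are handled.

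Either choice takes a few lines of SAP text and one derivation change, using assessments the protocol already schedules. Option 1 lowers the reported RFS slightly. With option 2 the estimate applies to a selected population and no longer describes everyone ablated.

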4.0 PROTOCOL SUMMARY

Full Title	A Multicenter Observational Registry to Develop Ablation Parameter Guidance for Microwave Liver Ablation of Soft Tissue Lesions
Protocol Number	NEU_2017_04
Short Title	NOLA (NeuWave Observational Liver Ablation) Registry
IDE/IND number	N/A
Sponsor	NeuWave Medical, Inc.
Indication	Ablation (coagulation) of soft tissue in percutaneous, open surgical, and in conjunction with laparoscopic surgical settings, including the partial or complete ablation of non-resectable liver tumors.
Registry Article Description	
 • NEUWAVE Microwave Ablation System and Accessories (originally marketed as the “Certus 240 140 2.45GHz Ablation System and Accessories”; hereafter referred to as “NEUWAVE Microwave Ablation System”). • NEUWAVE Microwave Ablation System with Ablation Confirmation.
Registry Design	This is a multicenter, observational registry that follows patients for a total of 5 years from the date of the first liver ablation procedure with the NEUWAVE Microwave Ablation System.
Sample Size	N = up to 1500 patients ablated.
Registry Population	Patients with at least one soft-tissue liver lesion ablated with the NEUWAVE Microwave Ablation System or NEUWAVE Microwave Ablation System with Ablation Confirmation.
Geographic Areas	Starting at sites in the United States and expanding to regions where NEUWAVE Microwave Ablation Systems are available, including EMEA and Asia.
Registry Duration	Enrollment: ~2 years Follow up: 5 years
Procedure(s) Description	Patients who meet the eligibility criteria will undergo microwave ablation (MWA) with the NEUWAVE Microwave Ablation System with or without Ablation Confirmation of at least one soft-tissue liver lesion, in accordance with the study site’s standard-of-care (SOC) practices.
Primary Objective	The primary objective of this registry is to compile data that will be analyzed at various timepoints, to understand the impact of selected parameters on procedure/patient outcomes.

Primary Endpoints	
 • Technical success (perioperative endpoint) • Technique efficacy (short term endpoint) • Target lesion recurrence (local recurrence) rate (long term endpoint)

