7.3 Inclusion Criteria

1. Patients who underwent or are scheduled to undergo a microwave ablation of one or more liver lesions with the NEUWAVE Microwave Ablation System per the device's Instructions for Use (IFU).
2. Patients with signed informed consent (or waiver approved by IRB/EC) who are willing to comply with the assessment schedule, and willing to have data included in the database.
3. Patients \geq 22 years old at the time of informed consent (or waiver approved by IRB/EC).

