12.1 Visit 1 – Screening

The screening assessments for this visit may occur over several dates within 60 days prior to Visit 2. If the patient is not seen within a 60 day window of the Ablation Day (Visit 2), the Screening Visit may occur on the same day as the ablation procedure.

Patients will be selected for microwave ablation based on the pre-procedure investigations and the Investigator's opinion. Eligible patients will be provided with the registry information, including the ICF.

The following screening assessments will occur within 60 days prior to the ablation visit (Visit 2):

- Patients must be given ample time to review and sign the ICF, or have a waiver in place, where applicable.
- Collect demographic information (age at time of Visit 1, sex, race, ethnicity).
- Collect patient parameters, as outlined in Section 19.1, subsection 2.
- Perform a liver tissue assessment (if available): steatosis (mild, moderate, severe); fibrosis/cirrhosis (mild, moderate, severe; include pathology results and fibrosis stage, if known); liver stiffness (actual stiffness value in kilopascals, if known); vascular invasion (presence or absence); microsatellite instability (MSI; high [MSI-H], low [MSI-L], or microsatellite stable [MSS]).
- BCLC staging, if applicable

- Evaluate Eastern Cooperative Oncology Group classification (ECOG) performance status.
- Body Mass Index (BMI): height and weight.
- Child-Pugh Score, if applicable and American Society of Anesthesiologists (ASA) Score.
- SOC imaging used to determine the ablation plans (CT, MRI, PET, Ultrasound (US), and/or X-ray), even if not within the screening window, should be used to determine soft tissue liver lesion details (e.g., lesion size, lesion type, location, shape).
 - If a Screening Visit occurs and the patient's SOC scans do not fall within the screening window, then an additional scan is not required for the screening visit.
 - For purposes of this Registry, target lesions are defined as any lesions ablated or intended to be ablated on the Ablation Day (Visit 2). Non-target lesions are defined as any lesions not ablated or not intended to be ablated on the Ablation Day (Visit 2).
 - All SOC scans of the abdomen/liver (CT, MRI, and/or PET) should be submitted to the Sponsor.
- Laboratory tests if applicable, per site SOC; to be done within 60 days of the ablation procedure,
 - Coagulation tests, including, INR, PT and APTT (or PTT).

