17.9 Analyses to be Conducted

Categorical variables will be summarized descriptively by frequencies and associated percentages. Continuous variables will be summarized descriptively by number of patients, mean, standard deviation, median, minimum, and maximum. Confidence intervals will also be provided for procedure-related variables.

Disposition of Registry Patients

Patient disposition will be summarized using counts and percentages. The number and percentage of patients completed and discontinued along with the specific reasons for discontinuation will be tabulated.

Demographic and Baseline Characteristics

Summary statistics will be provided for patient demographics and pre-operative ablation characteristics.

Primary and Secondary Endpoint Analyses

Regression analysis methodologies will be utilized to explore the relationship between dichotomous clinical outcomes (technical success, technique efficacy, and secondary efficacy rate) and ablation procedure, patient, and provider parameters. Time to event analyses will be used for target lesion recurrence, regional recurrence rate, recurrence-free survival, progression free survival, and overall survival.

Complete details regarding all analysis methodologies including approaches to handle multiple lesions per patient, variable selection techniques, data reduction techniques given the number of potential independent variables, as well as subgroup analyses of interest will be specified in the SAP.

The number and percentage of patients achieving technical success will be summarized and a 95% confidence interval will be provided. A similar summary will be provided for technique efficacy, as well as for the primary and secondary efficacy rates, as previously defined.

Target lesion recurrence rates at each post-ablation scheduled visit will be estimated using the Kaplan-Meier method and 95% confidence intervals will be provided. A similar summary will be provided for the 5-year overall rate. Similar summaries will also be provided for regional recurrence rate, overall and progression-free survival rates for the entire observation period from the ablation procedure date through 5 years of follow-up.

Scores from the EORTC QOL questionnaires and Numeric Pain Rating Scales will be summarized with methodology consistent to the recommendations of the specific survey. Additional endpoints will be summarized with descriptive statistics.

Plans for Interim Analysis

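### Recurrence-free survival pools patients cleared of liver disease with patients whose known lesions were left untreated, and growth of those lesions is not an event

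*SAP*

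**What the plan says.** Who enters the analysis:

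- Protocol 7.3 admits patients who have had, or will have, "microwave ablation of one or more liver lesions with the NEUWAVE Microwave Ablation System". It does not ask that every known lesion be treated.
- Protocol 12.1 sets the two lesion classes. A lesion treated at Visit 2, or planned for treatment then, is a target. For the other class the wording is "Non-target lesions are defined as any lesions not ablated or not intended to be ablated on the Ablation Day (Visit 2".
- SAP section 6 analyses the secondary endpoints in the FAS, meaning eligible patients in whom the device was used. Nothing there depends on whether known disease was left behind.

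What counts as an RFS event (SAP 8.6):

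- (a) recurrence of a target lesion, counted only from Visit 4 onwards
- (b) "Identification of a new non-target lesion during visit 3 to visit 14 including unscheduled visits at patient level"
- (c) any death while the patient is followed

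RFS is estimated by Kaplan-Meier at 3, 6 and up to 60 months. The regional recurrence event in the same section also requires a new lesion. SAP 8.5 removes patients who failed technique efficacy from the target lesion recurrence analysis; SAP 8.6 has no comparable rule for RFS. SAP 8.7 plans no sensitivity analysis.

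Protocol 17.9 also lists progression-free survival: "Similar summaries will also be provided for regional recurrence rate, overall and progression-free survival rates". The protocol does not define it, and the SAP does not analyse it.

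**The concern.** A reader takes an RFS rate after ablation to describe how long patients stay free of disease once treated. That needs a starting population that was free of known disease, at least in the liver. Here a patient with two known lesions, one ablated and one left, is counted as recurrence-free on Day 0. If the untreated lesion then grows, the patient stays recurrence-free until something else happens.

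The SAP accepts the underlying principle elsewhere: it drops patients whose target lesion was not fully ablated from the recurrence analysis, since what was never cleared cannot recur. RFS has no matching rule for patients whose liver was not cleared. The reported rate then depends partly on how many partly treated patients the sites enrolled, and nothing in the planned output reveals that number.

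**Working it through.** There is no planned RFS figure to reproduce. The documents give no expected rate, no event count, and no share of patients with untreated lesions. The check is a reading of the event rules, then the direction of the effect, then an illustration of size.

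**Step 1: follow one patient through the rules.** Lesions A and B are both known at screening. A is ablated at Visit 2. B is neither ablated nor intended to be. B later grows.

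| Time-to-event endpoint | Does growth of B count? |
|---|---|
| Target lesion recurrence (SAP 8.5) | No; B is not a target lesion |
| Regional recurrence (SAP 8.6) | No; B is not new |
| RFS (SAP 8.6) | No; not (a), because B is not a target; not (b), because B is not new; (c) is death |
| Overall survival (SAP 8.6) | No; death only |

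**Step 2: direction.** Let T be the time to the first SAP event and G the time to growth of a known untreated lesion. Let f be the share of FAS patients with such a lesion.

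- *Growth counted as an event.* Event time becomes min(T, G), which is never later than T. RFS falls or stays the same, so the SAP rate is too high or equal.
- *Affected patients excluded.* Restricted RFS − FAS RFS = f × (S_cleared − S_partial), where both S terms use the SAP events. The sign depends on which group does worse on those events, which the documents do not say.

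**Step 3: illustration.** Every input is an assumption: constant hazards; growth independent of other events; 12-month RFS in cleared patients of 0.70; hazard ratio m for SAP events in partly treated patients; 12-month growth probability pg.

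With m = 1, the 12-month gap from not counting growth is f × 0.70 × pg:

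| f | pg = 0.5 | pg = 0.8 |
|---|---|---|
| 0% | 0 | 0 |
| 5% | 0.05 × 0.70 × 0.5 = 1.8 points | 2.8 points |
| 10% | 3.5 points | 5.6 points |
| 20% | 7.0 points | 11.2 points |
| 30% | 10.5 points | 16.8 points |

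The gap narrows later, as other events accumulate. For f = 20%, m = 1 and pg = 0.8 it is 11.2 points at 12 months, 6.8 at 36 and 3.4 at 60.

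For exclusion with m = 1, S_cleared = S_partial and nothing changes. With m = 1.5, S_partial = 0.70^1.5 = 0.586, so:

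- f = 10%: FAS rate = 0.9 × 0.70 + 0.1 × 0.586 = 68.9%, against 70.0% restricted (SAP rate lower by 1.1 points)
- f = 20%: FAS rate = 0.8 × 0.70 + 0.2 × 0.586 = 67.7%, against 70.0% restricted (SAP rate lower by 2.3 points)

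**Step 4: scale.** With 1,500 patients, RFS of 70% and no censoring, the 95% interval half-width is 1.96 × √(0.70 × 0.30 / 1500) = 2.3 points. Under the m = 1 assumptions, a share of about 10% gives a growth gap (3.5 to 5.6 points) larger than that.

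**The case against.** **A stronger reading is tempting: that RFS is simply overstated, by f × S(t).** With f of 10% to 30% and S(12 months) of 0.4 to 0.6, all assumed, that is 0.1 × 0.4 = 4 to 0.3 × 0.6 = 18 points. The formula treats every partly treated patient as an event at time zero, which is neither exclusion nor counting growth when it occurs. Against exclusion the sign is open, as Step 2 shows. The documents do not support an unconditional claim of overstatement.

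**Growth of a never-treated lesion is progression, not recurrence, and the SAP states its three events openly.** This has force. It means the fault lies in the population to which the RFS label is attached more than in the event list. It does not explain why patients who were never clear should start as recurrence-free.

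**A growth event may not be derivable.** This stands. Protocol 12.3 and 12.4 call for lesion details when a recurrence is found, no growth criterion for non-target lesions is given, and central review covers only a subset of scans from prospectively enrolled patients. Fully retrospective patients are the hardest case.

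**Progression-free survival might have closed the gap.** That is conjecture, since protocol 17.9 does not define it. Its absence from the SAP is a separate discrepancy.

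**The device indication shows that known lesions are left behind.** A reader might infer this from "including the partial or complete ablation of non-resectable liver tumors", but the phrase describes how completely a tumour is ablated. The point rests on protocol 7.3 and 12.1.

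**The untreated lesion is not invisible everywhere.** True. Later ablation of a non-target lesion could enter secondary efficacy, which is a proportion. A lesion intended for ablation but not ablated is also labelled target, so its growth might fall under event (a). These patients can still have events through target recurrence, a new lesion or death.

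**The harm has little route into planned comparisons.** Also true. RFS is secondary and descriptive. SAP 8.8 limits subgroups to the primary endpoints, SAP 8.10 does not model RFS, and no comparison by site is planned. Distorted comparisons between disease types or sites are therefore not a consequence of any specified output.

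**Conclusion.** The point holds as a fault in which patients the RFS rate describes. Nothing in the protocol or SAP keeps patients with known untreated liver lesions out of the RFS analysis, and growth of those lesions is not an event in any time-to-event endpoint.

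The direction is conditional. The SAP rate is too high or equal against an RFS that counts residual disease or its growth, and of unknown sign against an RFS limited to cleared patients. The size cannot be found from the documents, because the share of affected patients is not given. The ranges above are illustrations that rest on assumed values of f, m, pg and the 12-month rate, and the effect vanishes if no patient is affected. This is a worthwhile, inexpensive correction to a secondary endpoint; it does not touch the primary endpoints.

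**What to change.** In SAP 8.6:

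1. Estimate RFS in FAS patients with no known liver lesion left untreated after Visit 2. Define this by whether each known baseline lesion was actually ablated or otherwise removed. Do not use the target label, because protocol 12.1 also gives it to lesions intended for ablation but not ablated.
2. Show the FAS estimate beside it.
3. Report the number of patients with untreated baseline lesions.

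Separately, reconcile protocol 17.9 with the SAP on progression-free survival: either define and analyse it, or state that it has been dropped and why. Count growth of a known non-target lesion as an event only if the collected data support it.

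The cost is SAP wording, one more table and a smaller RFS denominator with a wider interval. Event (b) already requires new lesions to be told apart from known ones, so the restriction relies on a distinction the SAP already needs. The restricted rate may be higher or lower than the FAS rate.
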